5.0 THERAPEUTIC/DIAGNOSTIC AGENTS

5.1 Study agent: ROPIVACAINE^{11, 25-28}

5.1.1 Source and Pharmacology: A local anesthetic. Mechanism of action is by blockade of both the initiation and conduction of nerve impulses by decreasing the neuronal membrane's permeability to sodium ions, which results in inhibition of depolarization with resultant blockade of conduction. The half-life is 5 to 7 hours when used as an epidural infusion and has a terminal half-life of 111 ± 62 minutes. It is metabolized by the liver and excreted through the urine.

5.1.2 Formulation and Stability: Supplied in single-dose containers in 2 mg/ml (0.2%), 5 mg/ml (0.5%), 7.5 mg/ml (0.75%) and 10 mg/ml (1%). Store at 20°C to 25°C.

In this study, the PDH pharmacy will prepare four (4) syringes from a single vial of the 5mg/ml (0.5%) ropivacaine at a dose of 2mg/kg/patient divided evenly into 0.5mg/kg/syringe with a maximum dose of a single 20 ml vial = 100 mg.

5.1.3 Guidelines for Administration: Doses are administered via local infiltration.

5.1.4 Supplier: Commercially available. See package insert for further information.

6.1 CRITERIA FOR SUBJECT ELIGIBILITY

6.2 Subject Inclusion Criteria

- Diagnosis of neuroblastoma as defined by the International Neuroblastoma Risk Group Staging System (INRGSS)²²
- 3 - 18 years of age
- Patient has had prior bone marrow procedures
- English speaking

6.3 Subject Exclusion Criteria

- History of allergy to investigational agent: ropivacaine or other amino amide analgesics
- History of allergy to standard agent: propofol
- Chronic daily opioid requirement
- Lansky/Karnofsky Score < 60
- Inability to comply with protocol requirements including refusal to forego pre-procedural opioid use
- Patient is receiving additional potentially painful interventions (e.g. central line insertion/removal) concurrent with the bone marrow procedure

7.0 RECRUITMENT PLAN

All consecutive eligible patients will be offered participation in this study by a physician in the Department of Pediatrics at Memorial Sloan Kettering Cancer Center. No patients will be identified by chart review or direct advertising. Every week, the Neuroblastoma Personal Office Assistant (POA) will circulate an email to the consenting investigators on this study that includes the name and medical record number of every neuroblastoma patient receiving a bone marrow procedure in the following week. Every day, the consenting investigators on this study are included on an email notice of new patients being seen by the Pediatric Neuroblastoma service. In this way, potential study participants will be identified for recruitment. The consenting professional will be responsible for explaining the study and obtaining written informed consent. Participants in the study will receive neither financial payment nor reimbursement. Eligible patients of all genders and racial groups will be equally offered enrollment in the study.

8.0 PRETREATMENT EVALUATION

Before each bone marrow procedure, the patient will be re-evaluated for continued eligibility. If the patient does not meet eligibility at the time of the scheduled bone marrow procedure, the intervention may be postponed until a subsequent bone marrow procedure when the patient meets eligibility criteria.

9.0 TREATMENT/INTERVENTION PLAN

Each enrolled patient will serve as his/her own control. On two bone marrow procedures, patients will receive either **intervention A** or **B**.

Each procedure will occur at approximately a two to four month interval. The timing of bone marrow procedures will be determined by the patient's clinical course.

In Intervention A, standard of care dosing and administration will be at the discretion of the anesthesiologist according to standard of care in the Department of Anesthesia at Memorial Sloan Kettering Cancer Center. In Intervention B, 2mg/kg of 0.5% ropivacaine will be drawn into

pre-filled syringes with a maximum dose of 20ml = 100mg. The physician performing bone marrow procedures will administer ropivacaine.

Ropivacaine will be injected into the subcutaneous tissue in an area approximately 1 cm in diameter. Subsequently, the ropivacaine will be administered to the periosteum in an area approximately 2-3 cm in diameter. Four pre-filled syringes will be provided and proceduralist physicians will be advised to administer one full syringe volume for each site (0.5mg/kg) with equal distribution between the subcutaneous and periosteal injection per site. Currently, propofol alone is the standard of care in the Department of Pediatrics at Memorial Sloan Kettering Cancer Center. While ropivacaine is a well described local anesthetic agent, the addition of ropivacaine to propofol to minimize post procedure pain is an experimental intervention.

10.0 EVALUATION DURING TREATMENT/INTERVENTION

Pain will be assessed in the post-anesthesia care unit (PRR). Directly upon emergence from anesthesia after the procedure and every 15 minutes subsequently, PRR nurses will use the Wong-Baker FACES® Pain Rating Scale (Appendix 1). Nurses will record patient-reported pain scores and administered analgesia in the Electronic Medical Record (EMR). Analgesia doses will be recorded at the time of administration. The PRR nurses will follow a standardized post-procedural algorithm (Appendix 2.1). Patients will recover in the PRR for approximately 30 to 90 minutes prior to discharge from MSKCC. In some instances, patients will be discharged from the PRR to the Neuroblastoma Clinic in the Pediatric Day Hospital (PDH). We anticipate that all patients will be discharged from MSKCC before 6 hours from the end of their procedure. In the unexpected case that a patient is admitted to the hospital for any reason during the study period (28 hours post-procedure), study investigators will provide the inpatient RN with the post-procedural opioid management algorithm (Appendix 2.1). Only if the admission is due to a study related life-threatening grade 4 toxicity, will the admitted patient be removed from the study as described in Section 13.0.

Families will be provided a 2 part, 12 item written questionnaire with 4 items and 8 items in each part, respectively (Appendix 3). They will be asked to complete Part 1 at 6 hours (+/- 1 hour) and Part 2 at 24 hours (+/- 4 hours) following the procedure. This questionnaire will have items regarding pain intensity and management to be answered at both time points. Families will be asked to follow a post-procedure pain management plan (Appendix 2.2). Post-procedural quality of life (QOL) will be assessed using a four-item questionnaire (Appendix 3) adapted from the NIH PROMIS® Parent Proxy Item Bank for Pain Interference and approved for use by the MSKCC Behavioral Research Methods Core Facility. These four questions will include the domains of physical recovery, emotional and social functioning. QOL will be assessed about 24 hours (+/- 4 hours) following the procedure. Principal Investigators, Co-Investigators, Investigators or appropriate clinic staff will call families 24-72 hours following procedure to obtain answers to the questionnaire.

11.0 TOXICITIES/SIDE EFFECTS

11.1 DEFINITION OF TOXICITIES:

- Common - Happens to 20-100 patients out of every 100
- Occasional - Happens to 4-20 patients out of every 100
- Rare - Happens to 3 or fewer patients out of every 100

11.2 LOCAL INFILTRATION OF ROPIVACAINE^{11, 25-28}

Common	Occasional	Rare
None	None	
• Allergic reaction with any route of administration• Arrhythmia with intravascular administration*• Seizure with intravascular administration* 
*Reported with inadvertent intravascular administration

12.0 CRITERIA FOR THERAPEUTIC RESPONSE/OUTCOME ASSESSMENT

12.1 To assess primary objective, we will determine and compare for each study intervention the percentage of patients who required opioid analgesia between the time of bone marrow procedure and 24 hours (+/- 4 hours) after the procedure.

12.2 For the secondary objectives:

- a) We will determine and compare for each study intervention the percentage of patients who used any non-opioid analgesia within 24 hours (+/- 4 hours) after bone marrow procedure.
- b) We will calculate and compare for each study intervention the total dose of opioid consumption within 24 hours (+/- 4 hours) of the bone marrow procedure using mg/kg/day morphine equivalent.

Drug	IV conversion factor	PO conversion factor
Morphine	10mg	30mg
Fentanyl	0.250mg (250mcg)	—
Hydromorphone	2mg	8mg
Oxycodone	—	20mg
Oxymorphone	1mg	10mg
Codeine	75mg	130mg
Methadone	1mg	2mg
Hydrocodone	—	30mg

c) We will also determine the time to the first opioid administration. The starting point for this time will be the time of transfer to the PRR which will be documented by the PRR RN. This time will be recorded on the parent worksheet by the PRR RN.

d) We will assess standardized pain scores at 3 time points: (1) the maximum recorded pain score in the PRR, (2) at 6 hours (+/- 1 hour) and (3) 24 hours (+/- 4 hours) after the bone marrow procedure. Pain scores 2 and 3 will be recorded by the parent after discharge from MSKCC. We will use the following validated pain scales: Wong-Baker FACES® Pain Rating Scale for patients between 3-18 years of age for patient-reported pain when asked by post-anesthesia recovery room nurses upon emergence from anesthesia and by inpatient nurses or family members in the outpatient setting upon discharge from the post-anesthesia recovery unit. We will compare pain scores between study interventions.

e) The QOL metric is a brief instrument that will assess post-procedural quality of life within 24 hours (+/- 4 hours) of the bone marrow procedure. This instrument assesses the following domains: sleep, physical functioning, emotional functioning and social functioning. This brief measurement tool will be adapted from a validated metric for pain interference in pediatric patients: NIH PROMIS® Parent Proxy Item Bank v1.0 – Pain Interference, which is a 13-item questionnaire. However, given that our study has rapid, frequent assessments, we will use an

abbreviated version for feasibility purposes and to minimize participant burden. Parents will be asked to assess QOL at 24 hours (+/- 4 hours) following the procedure by completing the questionnaire at that time. Principal Investigators or Research Staff will call families 24-72 hours following procedure to obtain answers to survey. This phone call will be for the purposes of data collection only and not for survey administration.

f) Patients will be under medical observation during the expected time when most adverse effects from ropivacaine will be experienced. Families will be advised to call the hospital for any symptoms beyond this time period.

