2.1 OBJECTIVES AND SCIENTIFIC AIMS

Primary Objective:

- Determine whether there is a reduction in the percentage of pediatric neuroblastoma patients undergoing a bone marrow procedure who require post-procedural opioid analgesia within 24 hours (+/- 4 hours) of the procedure with the addition of local ropivacaine.

Secondary Objective:

Determine whether there is a difference in:

- 24 hours (+/- 4 hours) post-procedure opioid consumption in morphine equivalents (mg/kg/day)
- Percentage of patients requiring non-opioid analgesia within 24 hours (+/- 4 hours) of procedure
- Standardized pain scores (Wong-Baker FACES® Scale)
- Time to first opioid medication
- Short-term quality of life
- Adverse outcomes with the addition of local ropivacaine

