3.3 Rationale

The purpose of this study is to investigate whether subcutaneous and periosteal infiltration of a local anesthetic agent, ropivacaine, will reduce the percentage of patients requiring post-procedural opioid analgesia and improve quality of life in the day following the procedure. A similar study recently demonstrated that topical analgesia for lumbar punctures reduced the amount of propofol used in pediatric oncology patients.⁹ However, no study has been done to investigate the efficacy of local analgesia in combination with propofol for bone marrow procedures. For this reason, a trial evaluating the effect of the addition of local analgesia is both justified and necessary. Local analgesia acts to limit the initiation of nociceptive pathways prior to the traumatic insult, in this case, subcutaneous and periosteal infiltration by a bone marrow aspiration or biopsy needle. Ropivacaine is an example of a local anesthetic agent that blocks both the initiation and conduction of nerve impulses by decreasing the neuronal membrane's permeability to sodium ions.¹⁰ It is an amino-amide local anesthetic that is a pure S-(-)-enantiomer with lower lipid solubility than racemic mixtures; these features allow ropivacaine to have a higher safety profile with less cardiovascular and central nervous system toxicity than racemic lidocaine and bupivacaine.¹⁰ Its onset of action is listed as "fast" with infiltration. i.e. within 3 to 15 minutes.¹¹ Its duration of action is 3 to 15 hours.¹¹ Therefore, due to its effect on nociceptive pathways, rapid onset and moderate duration of action while maintaining a low toxicity profile, ropivacaine is a reasonable option for local analgesia for bone marrow procedures. This is the first time ropivacaine will be directly injected into the bone marrow site at MSKCC Pediatrics.

Primary and secondary outcome measures were carefully selected after reviewing pediatric pain literature. Within pain clinical trials, analgesic efficacy can be measured by the ability to reduce or eliminate the need for rescue analgesia. "Rescue analgesia-sparing" has been identified as practical and feasible surrogate primary endpoint^{12,13}. A systematic review of

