4.1 OVERVIEW OF STUDY DESIGN/INTERVENTION

4.2 Design

This study will be a prospective double-arm randomized controlled single-blinded crossover design. The two interventions are:

- Intervention A: MSKCC standard of care
- Intervention B: MSKCC standard of care *plus* local analgesia with ropivacaine.

Pediatric neuroblastoma patients will be enrolled based on eligibility criteria and randomized to one of two arms representing a specific sequence of each intervention.

- Arm 1 (AB): standard of care only during the first procedure, then standard of care plus ropivacaine during the second procedure.
- Arm 2 (BA): Standard of care plus ropivacaine during the first procedure, then standard of care only during the second procedure.

Each patient will serve as his or her own control. The patients and parents will be blinded to the study arm. The procedural attending physicians and pharmacy will have to coordinate and administer the treatment agent (ropivacaine), and they will not be blinded to the study arm. The registered nurse (RN) in the procedure room will similarly not be blinded to the study. The Pediatric Day Hospital (PDH) Procedure Recovery Room (PRR) RNs will be blinded as they will also be responsible for data collection as described below. The study investigators who will be responsible for post-procedural data collection will similarly be blinded to the study combination.

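### Non-serious adverse events after discharge depend on families calling in; one symptom question on the existing 24-hour form would ask about them in both interventions

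*Combined protocol and SAP*

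**What the plan says.** Section 2.1 lists among the secondary objectives "Adverse outcomes with the addition of local ropivacaine". Section 14.0 plans to compare, by GEE for binary data, the overall rate of complications or major adverse events and the rates of specific adverse outcomes. It labels these analyses exploratory.

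Section 12.2(f) describes how the events become known. First, "Patients will be under medical observation during the expected time when most adverse effects from ropivacaine will be experienced". After that, "Families will be advised to call the hospital for any symptoms beyond this time period".

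Section 10.0 gives the timing: "Patients will recover in the PRR for approximately 30 to 90 minutes prior to discharge from MSKCC", with some patients going on to the clinic, and "We anticipate that all patients will be discharged from MSKCC before 6 hours from the end of their procedure". The same section puts the study period at 28 hours after the procedure.

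Families complete a written questionnaire after every procedure: Part 1 (4 items) at 6 hours and Part 2 (8 items) at 24 hours. It is described as asking about pain intensity and pain management at both times, and it includes four quality-of-life items at 24 hours. Staff telephone 24 to 72 hours after the procedure to obtain the answers. Section 12.2(e) says of this call: "This phone call will be for the purposes of data collection only and not for survey administration".

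The data list in Section 16.0 covers demographics, diagnosis, opiates, analgesia, pain scores and quality of life. Section 16.2 says adverse events will be tabulated by severity. Section 17.2 requires serious adverse event reporting until 30 days after the last intervention.

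**The concern.** A comparison of complication rates needs a method that finds complications in the same way, and reasonably completely, after each procedure. While the child is in the center, staff observe. After discharge, the described method for a non-serious symptom is that the family decides to telephone. Many mild symptoms would not prompt a call, so the count depends on how readily families ring.

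At stake is the credibility of a stated objective. Section 3.3 notes that this is the first direct injection of ropivacaine at the marrow site in this department, and Section 3.3 also presents it as having a low toxicity profile. A statement that few adverse events occurred is stronger if families were asked than if they merely did not call.

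**Working it through.** **No plan figure to reproduce.** The documents give no expected rate or power for adverse outcomes. The sample size concerns the primary endpoint: 45 evaluable patients, 50 enrolled. A re-computation with the exact conditional McNemar test (30% vs 10%, correlation 0.4, two-sided 0.05) gives power 0.809 at 45, and 45/(1 − 0.10) = 50. Nothing proposed here changes those numbers.

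**Time observed and time left to spontaneous calls** (Section 10.0, counted from the end of the procedure)
- In the center: under 6 of 28 hours, 6/28 = 21% at most.
- At home: at least 28 − 6 = 22 hours, 22/28 = 79%.

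These are shares of time, not of events.

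**Does the form ask about symptoms?** Part 1 has 4 items, described as pain and its management. Part 2 has 8, which fits 4 on pain and management plus the 4 quality-of-life items. The described content can therefore account for all 4 + 4 + 4 = 12 items. This is consistent with there being no symptom item, but it does not prove it, since the Appendix 3 wording is not shown.

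**Effect of equal under-counting.** Let the true rates be pA and pB, and let a share s of events be reported under each intervention.
- Observed rates are s·pA and s·pB, so both are understated.
- The risk difference becomes s(pB − pA).
- The rate ratio is unchanged, and the odds ratio changes little when events are rare.

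Example with assumed values (pA = 5%, pB = 10%, s = 0.5):
- The risk difference falls from 5 to 2.5 points.
- The true odds ratio is (0.10/0.90)/(0.05/0.95) = 2.11.
- The observed odds ratio is (0.05/0.95)/(0.025/0.975) = 2.05.

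**Illustration of capture.** The rates p and reporting shares s are assumed, not from the documents. With 50 procedures under one intervention, the chance of recording at least one case is 1 − (1 − p·s)^50:

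| True post-discharge rate | s = 25% | 50% | 75% | 100% |
|---|---|---|---|---|
| 3% | 0.31 | 0.53 | 0.68 | 0.78 |
| 5% | 0.47 | 0.72 | 0.85 | 0.92 |
| 10% | 0.72 | 0.92 | 0.98 | 0.995 |

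**Limit even with full capture.** If no event is seen in 50 ropivacaine procedures, the one-sided 95% upper limit is 1 − 0.05^(1/50) = 5.8%. With 45 procedures it is 1 − 0.05^(1/45) = 6.4%.

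**Coverage after the change.** A Part 2 question about the time since the procedure, answered at 24 ± 4 hours, covers 20 to 28 of 28 hours: 20/28 = 71% to 28/28 = 100%. A second question in Part 1 would not extend that coverage.

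**The case against.** The plan has a reason for its approach. Section 12.2(f) expects most ropivacaine effects to occur under observation. Section 11.2 lists no common or occasional toxicities. It lists only rare ones: allergic reaction, and arrhythmia or seizure after inadvertent intravascular injection. The drug is given before the aspirations, with an anesthesiologist in attendance, so observation after injection is longer than the recovery stay alone. Families are told to call about any symptom, charts are reviewed, and serious events are reported for 30 days. The analysis is exploratory, and an open question will also collect symptoms unrelated to ropivacaine.

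Most of this stands, and it limits the point to mild events at home. It does not answer that point. Section 14 compares complications of every kind, not only ropivacaine effects. Section 16.2 says how events are tabulated, not how a non-serious event at home becomes known, and chart review finds only what reached the chart.

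A reader might infer more, in four ways that the documents do not support:
- **That toxicity outlasts observation.** Section 3.3 says "Its duration of action is 3 to 15 hours", but that describes the anesthetic effect and is not a toxicity window.
- **That 79% of the risk is unmonitored.** The figure is a share of hours, and the plan expects most ropivacaine effects early.
- **That the comparison is biased toward ropivacaine.** Patients and parents are blinded, and Section 4.2 adds: "The study investigators who will be responsible for post-procedural data collection will similarly be blinded to the study combination". Under-counting need not differ between interventions.
- **That the call bars recording a symptom.** The restriction in Section 12.2(e) concerns how questionnaire answers are obtained; staff may still note what a parent mentions.

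**Conclusion.** The point holds as a low-priority improvement. For non-serious events after discharge, the described method is spontaneous calling over at least 22 of the 28 study hours, although adverse outcomes are an objective with a planned comparison. Mild events would probably be under-counted in both interventions. Absolute rates and any risk difference would be understated and precision lost; the odds ratio would change little if under-counting is equal and events are rare.

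The number missed cannot be estimated, because the documents give neither a rate for mild events nor a reporting share. Serious or acute toxicity would probably be caught by observation and serious adverse event reporting. The primary endpoint, sample size and power are unaffected, and the safety comparison remains imprecise even with full capture.

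The conclusion assumes that Appendix 3 contains no symptom item. If it already has one, only the omission from the Section 16.0 list remains.

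**What to change.** 1. Add to Part 2 of the questionnaire (24 hours) one question asking whether the child has had any other symptoms or problems since the procedure, and when. Use the same wording after both interventions, have the blinded family answer it, and collect the answer at the existing 24 to 72 hour call. A matching item in Part 1 (6 hours) is optional: it may help recall but adds no time coverage.
2. Add adverse events to the Section 16.0 data list.

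The form grows from 12 to 13 items per procedure (14 with the optional item), and a wording amendment is needed. There is no new visit or call. The costs are a little more burden on families, in a plan that shortened its quality-of-life instrument to limit burden, and background symptoms that must be recorded and attributed.
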